10.2. Sensitivity of Primary Endpoint

The following two sensitivity analyses will be performed:

- a) This sensitivity analysis will be based on the PP Set, and the primary endpoint (mean change pain severity as assessed by an 11-point NRS, from baseline to Week 16), will be analysed using similar MMRM approach as specified in [Section 10.1](#). No imputation will be performed in this analysis.
- b) This sensitivity analysis will be based on the FAS population. Missing records of subjects who prematurely discontinued the randomly assigned study drug, will be imputed with the worst value from baseline before drop out within each subject. Intermittent missing data will not be imputed and all missing values after discontinuation will be imputed. The worst value is the highest pain score from baseline to before drop out. Change from baseline for the imputed Week 16 value will then be calculated as imputed Week 16 - baseline. For example in the following case:

3 1 x 2 3 y y

where x and y are missing data, the imputation will complete y values but not x as it is the intermittent missing data.

The primary endpoint (mean change in pain severity as assessed by an 11-point NRS, from baseline to Week 16), will be analysed by using a repeated measures analysis

of covariance (ANCOVA) for the imputed population, using visit on subject ID as the repeated factor with unstructured covariance term (REPEATED VISIT/SUBJECT=SUBJID TYPE=UN). If convergence is not achieved then other covariance structures will be investigated such as compound symmetric (TYPE=CS). The model will include fixed effects terms for treatment, country, and visit, and covariate term for pain severity score at baseline.

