9.2. Sample Size Determination

On the basis of previous post-hoc analyses of pain (Cattaneo et al 2017) and of similar studies (Folstein et al, 1975), it is anticipated that a sample size of 144 participants would permit detection of a 1 point treatment difference in the NRS between safinamide and placebo assuming a standard deviation of 2, 5% significance and 80% power. A 1 point treatment difference is considered to be a clinically meaningful treatment effect (Rascol et al, 2016).

Approximately 220 participants will be screened to achieve 177 randomly assigned to study intervention and of which approximately 144 participants complete the study (96 and 48 evaluable participants in the active and placebo group respectively).

Since March 2020, the COVID-19 emergency has impacted the feasibility of the trial, which is being conducted in a vulnerable group of patients. Upon receipt of the guidance “Statistical Considerations for Clinical Trials During the COVID-19 Public Health Emergency” issued by FDA on June 2020, released with the aim of helping sponsors ensure that trials conducted during the Covid-19 emergency could continue, where appropriate, to provide interpretable findings with correct statistical quantification of uncertainty, the Sponsor performed a Blind Data Review Analysis of the primary endpoint data (pain severity) for the 26 patients who had completed the study as of June 2020.

The results of the analysis show that the standard deviation used in the original sample size estimation (SD = 2. was a conservative overestimate of the observed SD from the actual trial data, which is 1.43.

Based on this, the Standard Deviation, for the estimation of sample size has now been amended to 1.50, and the power has been maintained as 80%. New sample size estimates have been performed considering different magnitudes of Treatment Difference, but keeping the same assumptions of screen failure rates and drop out rates. These are summarized below in Table below

| SCENARIO | SAMPLE SIZE |
|--|---|
| Power = 80% Standard deviation = 1.5 Treatment Difference = 1 point | Pts to screen= 132 Pts to randomize= 105 Pts completing study= 84 |
| Power = 80% Standard deviation = 1.5 Treatment Difference = 1.5 points | Pts to screen= 66 Pts to randomize= 51 Pts completing study= 39 |
| Power = 80% Standard deviation = 1.5 Treatment Difference = 2 points | Pts to screen= 39 Pts to randomize= 30 Pts completing study= 24 |

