10.1. Primary Efficacy Endpoint

Pain severity data will be derived from the daily diary.

The primary endpoint evaluated in this study is the mean change in pain severity (“average worst pain experienced in the last 7 days”, i.e. average of the worst pain score on each of the 7 days preceding the site visit), as assessed by an 11-point NRS, from baseline to Week 16. For efficacy analysis, at least 4 out of 7 daily pain scores are needed to calculate a valid average over 7 days.

The null hypothesis for the primary endpoint is that safinamide is no better than placebo in managing pain; thus $\mu(\text{Safinamide}) > \mu(\text{Placebo})$, where μ represents the population mean change in pain severity score from baseline at Week 16 and a negative change would indicate improvement.

The primary efficacy endpoint, change from baseline to Week 16 in pain severity score, will be analysed using a mixed model repeated measures (MMRM) using visit on subject ID as

the repeated factor with unstructured covariance term (REPEATED VISIT/SUBJECT=SUBJID TYPE=UN). If convergence is not achieved, then other covariance structures will be investigated such as compound symmetric (TYPE=CS). The model will include fixed effects terms for treatment, country, visit and regular pain medication use at baseline (yes or no) and covariate term for pain severity score at baseline. The method above (e.g. MMRM) is unbiased under the MAR assumption and can be thought of as aiming to estimate the treatment effect assuming that after withdrawal, subjects would have continued on a similar trajectory to their peers in the same arm who have the same covariates.

The likelihood-based mixed-effect model repeated measure will be performed using a SAS PROC MIXED procedure, and the Kenward-Roger method for degrees of freedom will be applied. The restricted maximum likelihood (REML) method will be used for estimation. The least square (LS) means of change from baseline in pain severity along with the associated SE and 95% CIs will be calculated from the model at each time point. The LS mean difference between the treatment groups at Week 16 will also be reported, along with the corresponding SE, 95% CIs, and the p-value derived for the difference between treatment arms (safinamide – placebo). No adjustment is being made for multiple comparisons.

Results for time points other than Week 16 (Weeks 4 and 8) will be presented in both the above discussed model-adjusted and descriptive forms.

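### Sensitivity analysis (b) omits the primary model's regular-pain-medication term, so its difference from the primary result cannot be attributed solely to the missing-data assumption

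*SAP*

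**What the plan says.** SAP 10.1 gives the primary MMRM "fixed effects terms for treatment, country, visit and regular pain medication use at baseline (yes or no", with baseline pain severity as a covariate. Protocol 9.4.1 lists the same terms. SAP 10.1 also explains the missing-data assumption: after withdrawal, patients are taken to have "continued on a similar trajectory to their peers in the same arm who have the same covariates".

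SAP 10.2 plans two sensitivity analyses.

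- Analysis (a) uses the Per Protocol set without imputation, "analysed using similar MMRM approach as specified in" Section 10.1, so it keeps the pain-medication term.
- Analysis (b) stays on the FAS and changes the missing-data rule: "Missing records of subjects who prematurely discontinued the randomly assigned study drug, will be imputed with the worst value from baseline before drop out". Intermittent gaps stay missing. It uses the same repeated-measures structure and covariance fallback as the primary model, but lists the terms afresh: "The model will include fixed effects terms for treatment, country, and visit, and covariate term for pain severity score at baseline".

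Regular pain medication use does not appear in that list. SAP 10.2 gives no reason, and SAP Section 12 on changes to the planned analysis offers none. Section 10.2(b) also does not restate REML or Kenward-Roger.

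**The concern.** Analysis (b) is the only planned analysis of the primary endpoint that replaces the missing-at-random assumption with a less favourable one. Analysis (a) changes the population and imputes nothing. Analysis (b) is therefore where a reader will look to see how far the result depends on dropout.

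For that reading, only the handling of missing values should differ from the primary analysis. Here the adjustment set differs as well. No planned analysis fits the imputed data with the covariate, or the unimputed FAS data without it, so the planned outputs cannot separate the two changes. The covariate also belongs to the assumption under test, because the primary analysis conditions on patients with the same covariates. In (b) it would still bear on the intermittent gaps, which are left to the model.

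Neither Protocol 6.3 nor SAP 4.2 describes stratification by pain medication use. Some chance imbalance between the arms should be expected, and removing the term lets that imbalance into the estimate.

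**Working it through.** **1. The plan's own figures.** Protocol 9.2 and SAP 4.1 use SD 1.5, a difference of 1 point, 80% power and 2:1 allocation. A 5% level is stated in the same sections; two-sided is assumed here. A noncentral-t calculation gives 28 placebo and 56 active patients, total 84, with power 81.2%. Implied dropout is 1 − 84/105 = 20%, and 84/0.80 = 105. The stated 84 and 105 reproduce. At 2:1, 105 randomised means 70 and 35.

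**2. The two models side by side.**

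| Element | Primary (SAP 10.1) | Analysis (b) (SAP 10.2) |
|---|---|---|
| Analysis set | FAS | FAS |
| Covariance | Unstructured, with fallback | Unstructured, with fallback |
| Treatment, country, visit, baseline pain | Yes | Yes |
| Regular pain medication at baseline | Yes | **No** |
| Values after discontinuation | Left missing (MAR) | Worst observed value |
| REML, Kenward-Roger | Stated | Not restated |

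**3. Size of the shift from dropping the term.** The shift is approximately g × (between-arm difference in the proportion of users), where g is the difference in pain change between users and non-users given the other model terms. Under randomisation its mean is zero and its SD is g × √[p(1−p)(1/70 + 1/35)], with p the share of users. The documents give neither g nor p; both are assumptions.

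- p = 0.5: √(0.25 × 0.04286) = 0.104
- p = 0.3 or 0.7: √(0.21 × 0.04286) = 0.095

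The share of outcome variance explained is R² = g²p(1−p)/1.5². The SE is 1.5 × √(1−R²) × √(1/70 + 1/35) with the term, and 0.311 without it.

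| g (points) | SD of shift, p = 0.3 or 0.7 | SD of shift, p = 0.5 | 95% range, p = 0.5 | R², p = 0.5 | SE with term, p = 0.5 | SE without |
|---|---|---|---|---|---|---|
| 0.5 | 0.047 | 0.052 | ±0.10 | 3% | 0.306 | 0.311 |
| 1.0 | 0.095 | 0.104 | ±0.20 | 11% | 0.293 | 0.311 |
| 1.5 | 0.142 | 0.155 | ±0.30 | 25% | 0.269 | 0.311 |

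**4. Comparison with the imputation effect.** This used 4,000 simulated trials of 70:35 with a true difference of −1 at Week 16, change SD 1.5 and half the patients regular users. Dropout was 20%, equal in expectation between arms and unrelated to outcome, after Week 4 or Week 8. Worst-value imputation followed the rule in 10.2(b). A Week 16 ANCOVA stood in for the repeated-measures model, with completers only in place of the primary analysis.

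| g | Shift from imputation alone: mean (SD) | Shift from dropping the term: mean (SD) | Trials where the covariate shift exceeds the imputation shift |
|---|---|---|---|
| 0.5 | +0.154 (0.177) | 0.001 (0.056) | 11% |
| 1.0 | +0.158 (0.176) | −0.002 (0.094) | 20% |

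The imputation moves the estimate towards zero on average. Dropping the term does not move it on average but adds scatter. The case g = 1.5 was not simulated.

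**The case against.** The strongest reply is that little depends on this. Under randomisation, omitting a baseline covariate introduces no expected bias, and the imputation shift is systematic and one-directional. A reader who sees (b) move towards zero will usually be right to credit the imputation. The model in (b) still adjusts for baseline pain and country, which may carry much of what pain medication use would add. No decision rule is tied to (b), and nothing in the SAP requires a sensitivity analysis to vary only one element.

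Most of this stands, and it limits the point. Two stronger readings are tempting and should be refused:

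- A reader might infer that a difference between (b) and the primary result says nothing about dropout. It does; it cannot be credited to dropout alone.
- A reader might infer that the covariate shift is as large as the imputation shift. That compares the SD of a zero-mean shift with a mean shift, and the two match only at about g = 1.5 with 50% users. There, one yes/no variable would explain 0.5625/2.25 = 25% of the variance in change, and nothing in the documents supports such a value.

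What the reply does not remove is that the omission is unexplained in an otherwise parallel paragraph, and that in the one trial actually run the reader will see a single number mixing two changes.

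**Conclusion.** The point holds in a limited form. Analysis (b) changes the imputation and the adjustment set together, so its difference from the primary result cannot be attributed solely to the missing-data assumption. The omission adds no expected bias. It adds zero-mean noise with SD about 0.05 to 0.10 NRS points at 70:35 for an assumed covariate effect of 0.5 to 1.0 point, rising to about 0.16 at 1.5 points. The SE grows from 0.306 to 0.311 at an effect of 0.5, and from 0.293 to 0.311 at 1.0, with 50% users.

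This is usually smaller than the imputation effect of about 0.15 to 0.16. That comparison rests on equal, non-informative 20% dropout and a simplified model, and other dropout patterns would change it. The fact of the omission is certain from the text; its size depends on a user share and a covariate effect that the documents do not give. A reader might infer that the main result is compromised. It is not: the primary analysis, alpha and sample size are untouched. This is a free improvement to a supportive analysis.

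**What to change.** In SAP 10.2(b), replace the list of model terms with a cross-reference. It should say that the model is identical to that of Section 10.1, including regular pain medication use at baseline, REML estimation and Kenward-Roger degrees of freedom, and that only the handling of missing post-discontinuation values differs. The covariate part of the difference from the primary result is then removed by construction, with equal or slightly better precision.

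If the omission is deliberate, give the reason and add one bridging fit: either the imputed data with the term, or the primary analysis without it.

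The cost is one SAP sentence. The covariate is already derived for the primary model, so no new data are needed.

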10.3. Secondary Efficacy Endpoints

The PGI-C, CGI-C, CGI-S, and MDS-UPDRS will be analysed at weeks 4, 8 and 16 using the same statistical methods i.e. MMRM as for the primary efficacy parameter defined in [Section 10.1](#) by replacing covariate of pain severity at baseline with respective efficacy parameter

Pain severity score at Weeks 4 and 8 will also be analysed by the same MMRM method used for Pain severity score at Week 16 as defined in [Section 10.1](#)

Change from baseline in HADS at Week 16 will be analysed using an ANCOVA. The model will include treatment, baseline HADS and country as fixed effects. The Least Square (LS) means of the change from baseline in HADS score along with the associated SE and 95% CIs will be calculated, and the p-value derived for the difference between treatment groups at Week 16 will be presented.

Percentage of pain responders defined as subjects with reduction in pain severity of ≥ 2 points (“average worst pain experienced in the last 7 days”) as assessed by an 11-point NRS, compared to baseline), will be analysed at weeks 4, 8 and 16 using a Cochran-Mantel-Haenszel adjusted test of the difference in proportions between the two treatment groups. Country will be used as the stratification factor. A 95% confidence interval of the difference in proportions and p-value will be reported. For percentage of pain responders, a missing value at each visit will be imputed to indicate that a subject was a non-responder i.e. a Worst-Case imputation. It will be summarized for both Observed data and Imputed data.

The analysis of amount of concomitant PRN PD pain medications (as reported in the Patient Diary) and concomitant pain drugs (as reported on the ‘Concomitant Medications’ eCRF page) will be summarized in two ways i.e. the number of days on which pain medication was taken in the 7 days preceding Visits at Weeks 4, 8 and 16 and the number of patients taking pain medication in the 7 days preceding Visits at Weeks 4, 8 and 16.

The number of days that pain medication was taken will be analysed using a two-sided Mann Whitney test at the 5% level of significance level to test the null hypothesis of no difference between the two treatments. In case if the patient has not taken any pain medication in the 7

days preceding Visits at Weeks 4, 8 and 16, then the number of days will be considered as zero for that particular patient for that particular visit.

The percentage of patients using pain medication will be analysed using a Cochran-Mantel-Haenszel (CMH) adjusted test of the difference in proportions between the two treatment groups. Country will be used as the stratification factor. A 95% confidence interval of the difference in proportions and p-value will be reported.

11. Safety Analysis

All analyses of safety will be conducted using the Safety Set.

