4.1. Sample Size

On the basis of previous post-hoc analyses of pain (Cattaneo et al 2017) and of similar studies ([Folstein et al, 1975](#)), assuming a standard deviation of 2 it is anticipated that a sample size of 144 subjects would permit detection of a 1 point treatment difference in the NRS between safinamide and placebo at the 5% significance level with 80% power. A 1-point treatment difference is considered to be a clinically meaningful treatment effect ([Rascol et al, 2016](#)).

Approximately 220 subjects will be screened to achieve approximately 177 randomly assigned to study treatment and of which approximately 144 subjects completing the study (n= 96 and n= 48 evaluable subjects in the active and placebo group respectively).

Since March 2020, the COVID-19 emergency has impacted the feasibility of the trial, which is being conducted in a vulnerable group of patients. Upon receipt of the guidance “Statistical Considerations for Clinical Trials During the COVID-19 Public Health Emergency” issued by FDA on June 2020, released with the aim of helping sponsors ensure that trials conducted during the Covid-19 emergency could continue, where appropriate, to provide interpretable findings with correct statistical quantification of uncertainty, the Sponsor performed a Blind Data Review Analysis of the primary endpoint data (pain severity) for the 26 patients who had completed the study as of June 2020.

The results of the analysis show that the standard deviation used in the original sample size estimation (SD = 2) was a conservative overestimate of the observed SD from the actual trial data, which was 1.43 at the time of the blinded data review.

Based on this, the Standard Deviation, for the estimation of sample size has now been amended to 1.50, and the power has been maintained as 80%. New sample size estimates have been performed considering different magnitudes of Treatment Difference but keeping

the same assumptions of screen failure rates and dropout rates. These are summarized below in [Table 4.1](#).

Table 4.1 Sample Size Estimations

SCENARIO	SAMPLE SIZE
Power = 80% Standard deviation = 1.5 Treatment Difference = 1 point	Pts to screen= 132 Pts to randomize= 105 Pts completing study= 84
Power = 80% Standard deviation = 1.5 Treatment Difference = 1.5 points	Pts to screen= 66 Pts to randomize= 51 Pts completing study= 39

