4.2. Randomisation, Stratification, and Blinding

Subjects will be randomised to double-blinded treatment in a 2:1 ratio to receive either safinamide or placebo at Visit 2 (day 1). An interactive web response system (IWRS) will be used for the randomisation. PPD Biostatistics will generate the randomisation schedule for IWRS, which links sequential subject randomisation numbers to treatment codes.

In case of an emergency, the investigator has the sole responsibility for determining if unblinding of a subject's treatment assignment is warranted and should make every effort to contact the sponsor prior to unblinding a subject's treatment assignment unless this could delay emergency treatment of the subject. If a subject's treatment assignment is unblinded,

the sponsor must be notified within 24 hours after breaking the blind. The date and reason that the blind was broken must be recorded in the source documentation and case report form, as applicable.

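### The responder test adjusts for country only; adding baseline pain and regular pain medication use would be a cheap gain in precision, though the planned test is valid

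*SAP*

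**What the plan says.** SAP 10.3 defines responders as "subjects with reduction in pain severity of ≥ 2 points" relative to baseline. At each post-baseline visit (Weeks 4, 8 and 16) the arms are to be compared "using a Cochran-Mantel-Haenszel adjusted test of the difference in proportions between the two treatment groups. Country will be used as the stratification factor". Protocol 9.4.1 specifies the same test. On missing data SAP 10.3 says "a missing value at each visit will be imputed to indicate that a subject was a non-responder", and then adds "It will be summarized for both Observed data and Imputed data".

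The primary mixed model in SAP 10.1 uses the same diary score with "fixed effects terms for treatment, country, visit and regular pain medication use at baseline (yes or no) and covariate term for pain severity score", the covariate being the baseline value. Elsewhere in SAP 10.3, CGI-S and MDS-UPDRS enter the same model with their own baseline in place of baseline pain, and HADS has an ANCOVA with baseline HADS.

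SAP 4.2 says "Subjects will be randomised to double-blinded treatment in a 2:1 ratio to receive either safinamide or placebo". Despite its title, that section names no stratification factor. The documents give no responder rates, no power for this endpoint, no number of countries and no correlation between baseline pain and change.

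**The concern.** Response is a threshold on change from the patient's own baseline, so baseline pain is a natural predictor of it. A patient who starts higher has more room to fall. Protocol 5.2 also excludes scores of 4 or less at randomisation, which makes regression to the mean plausible. Of the pain-severity comparisons in the plan, the responder test is the only one that leaves baseline pain out.

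Two things are at stake. The first is precision: a predictor that the trial already collects goes unused. The second is chance imbalance. Nothing described in the design balances baseline pain between arms, and the placebo arm has about 35 patients. Any imbalance passes into the responder difference but is adjusted for in the primary analysis, so the two results can drift apart for that reason as well as others.

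**Working it through.** **1. The plan's own sample size.** Inputs from SAP 4.1: difference 1, SD 1.5, 80% power, 5% level (two-sided assumed), 2:1 allocation.
- Normal approximation: placebo n = (1 + 1/2) × (1.960 + 0.842)² × 1.5² / 1² = 26.5, so 27 + 54 = 81.
- Noncentral t: 28 + 56 = 84, power 0.812. This matches the plan.
- Dropout: 84 / 0.80 = 105, or 70:35.

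The plan's figure is reproduced. It sizes the primary endpoint only.

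**2. Implied responder rates.** Assume a normally distributed change with SD 1.5 and a true difference of 1. Then P(response) = Φ((-2 - mean change)/1.5). The placebo mean change is an assumption.

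| Placebo change | Placebo | Safinamide |
|---|---|---|
| 0 | Φ(-1.33) = 9% | Φ(-0.67) = 25% |
| -1.0 | Φ(-0.67) = 25% | Φ(0) = 50% |
| -1.5 | Φ(-0.33) = 37% | Φ(0.33) = 63% |

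Unadjusted two-proportion power with 84 completers is 40-62% over this range. At a placebo change of -1.0, counting 20% as non-responders gives 0.8 × 25% = 20% against 0.8 × 50% = 40%. The country-stratified test (CMH) then has simulated power of about 50-54% with 105 randomised.

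**3. Gain from adjustment.** These are simulations of 3,000 to 4,000 trials per setting. The assumptions not in the documents are the correlation of baseline with change, the effect of analgesic use, the placebo change, the baseline distribution, and the number and sizes of countries. The table gives the change in power, in percentage points, relative to the country CMH. The logistic columns cover both 84 completers and 105 randomised with 20% non-response. The last column is for 105 randomised.

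| Correlation | Logistic score test, nominal | Logistic, matched type I error | Adjusted risk difference, HC3 errors |
|---|---|---|---|
| 0 | about +2 | -2 to 0 | about 0 |
| -0.3 | +2 to +6 | -2 to +2 | +1 to +2 |
| -0.4 | not tabulated | not tabulated | +2 to +5 |
| -0.5 | +7 to +11 | +1 to +7 | +4 to +6 |

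Simulated type I error was 4.4-5.7% for the CMH, 5.4-7.9% for the logistic score test and 4.1-4.6% for the risk difference with HC3 errors. Much of the logistic test's nominal gain is therefore excess type I error. The last column is the fair comparison. Monte Carlo error is 1-2 points or more, so small gains are not distinguishable from zero.

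**4. Chance imbalance.** With an assumed baseline SD of about 1.2, the standard error of the between-arm difference in mean baseline is 1.2 × √(1/70 + 1/35) = 1.2 × 0.207 = 0.25 point. An imbalance above 0.25 point occurred in 31% of simulated trials. At correlations of -0.3 to -0.5, each point of imbalance moved the unadjusted risk difference by 7-12 percentage points. An imbalance of 0.25 therefore moves it by 0.25 × 7 = 1.75 to 0.25 × 12 = 3 points, against an expected effect of 40 - 20 = 20 points. Adjustment removed this shift.

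**5. Alternatives.** Stratifying the CMH more finely (country × analgesic use × baseline half) lost 0-9 points of power, so it is not the remedy. Country strata holding one arm only cost about 1 patient (6 assumed countries) to 4.5 patients (10 assumed) out of 105, which is minor.

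**The case against.** The strongest reply is that the CMH is valid, prespecified and identical in protocol and SAP. Chance imbalance is not bias under randomisation. Adjusted analyses of pain severity already exist at Weeks 4, 8 and 16. The responder and primary results can differ anyway, because one dichotomises and counts missing as failure while the other assumes data missing at random. A regression with several country terms and only about 7 placebo responders (35 × 20%) is also fragile. All of this stands, and it is why the point is an improvement and not a correction. It does not remove the case for using a covariate already in hand, provided that the method controls type I error.

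Three stronger readings are tempting, and the documents do not support them.
- A reader might infer a definite loss of 4 to 8 points of power. That figure needs a correlation the documents do not give. It also arises partly from comparing the CMH with a slightly liberal logistic test that pools countries, which shows a gain of 2 to 4 points even when baseline pain is irrelevant.
- A reader might take responders as the main secondary endpoint because they are listed first. The secondary endpoints are not ranked, there is no testing hierarchy, and no power is claimed for this one.
- A reader might think the tested dataset is undefined. SAP 10.3 says missing values will be imputed as non-response, and the observed-data version reads as an additional summary. One clarifying sentence is enough.

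**Conclusion.** The point holds as an efficiency suggestion. The responder test omits two baseline covariates that the primary model uses, and nothing in the plan explains the difference. The CMH remains valid. The power forgone at controlled type I error is about 0 to 6 points for correlations between 0 and -0.5. It is near 0 if the correlation is weak, 1-2 points at -0.3, 2-5 at -0.4 and 4-6 at -0.5, and a stronger correlation would give more. Adjustment also removes a shift of roughly 2-3 percentage points from a typical chance imbalance in baseline pain. These sizes rest on the plan's difference of 1, SD of 1.5, 2:1 allocation and 20% dropout. They also rest on assumed values for the correlation, placebo change, baseline spread and country mix.

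**What to change.** Before unblinding, amend SAP 10.3 as follows.
1. State that the responder comparison is tested on the non-responder-imputed data and that the observed-data version is supportive.
2. Prespecify a covariate-adjusted (standardised) risk difference with 95% CI, for example from a linear model of response on treatment, baseline pain severity, regular pain medication use and country, with HC3 or similar small-sample robust standard errors. Fix the rule for pooling small countries on blinded data.
3. Keep the country-stratified CMH as a supportive analysis.
4. Do not rely on an unpenalised logistic score test, which runs slightly above 5% at this sample size, and do not add strata to the CMH.

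Protocol 9.4.1 also names the CMH, so record the change in SAP section 12. The cost is wording and one extra model using covariates the primary analysis already needs. The downside is little or no gain if baseline pain barely predicts response.
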